# **Participant Dropout**

Dropouts and participants whose wound care ends or changes substantially prior to the anticipated 7day study period will be handled on an intent-to-treat manner in all key analyses with the last data obtained treated as the endpoint for that participant. Reasons for dropout will be recorded and contrasted across group.

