#### 1. Sample Size Estimate Based on Stay $\geq$ 7 days in Burn ICU.

The sample size calculation is based on the primary statistical procedure for this project which will test the difference in mean pain scores, defined as the average self-report of mean pain score, based on the Numeric Analogue Scale (NAS), during each burn wound care procedures, between individuals randomized to usual care plus placebo (fentanyl plus saline) and those randomized to the intervention arm (usual care + ketamine). PASS Sample Size (Version 14) was used to perform all sample size calculations while considering individuals over the one-year study duration randomized to control and intervention arms in a 1:1 fashion.

In the first case, we further assume that each individual, will, on average, have a length of stay of 7 days thus resulting in 14 wound care procedures performed during hospital stay. We determined the minimum sample size for our trial based on 80% power at p = 0.05 to detect a clinically significant difference in mean pain score during the wound care procedure of 2.0 points between the control and intervention arms with a standard deviation of 3.0. In addition, to account for the clustered nature of procedures performed on individuals, we have used a sample size inflator (also termed "design effect") of 10.1 as described by the Cochrane manual@ conservatively using an interclass correlation of effects of 0.7 amongst repeated measures of pain scores within each individual and 14 observations per individual.

The required sample size needed to accept the alternative hypotheses that the mean pain care score in the intervention arm decreased by 2 points compared to the control arm at the 0.05 level would require 27 individuals per arm (54 total), our anticipated population of 74 eligible individuals is adequate to show a clinically significant improvement for both intervention arms.

@http://handbook.cochrane.org/chapter\_16/16\_3\_4\_approximate\_analyses\_of\_cluster\_randomized\_trials\_for\_a.htm

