#### 2. Corrected Sample Size Estimate for Length of Stay on the Burn ICU $\geq$ 7 days as **estimated on Admission** but, however, where the **Actual Length of Stay on Burn ICU is** $\geq$ **5.5 days** because of Factors that either not present or not evident or were difficult to quantify at time of admission and consent of the patient.

This sample size calculation is based on the primary statistical procedure for this project which will test the difference in mean pain scores, defined as the average self-report of mean pain score, based on the NAS, during each burn wound care procedures, between individuals randomized to usual care (fentanyl plus saline) and those randomized to the intervention arm (usual care + ketamine). PASS Sample Size (Version 14) was used to perform all sample size calculations eligible individuals over the one-year study duration randomized to control and intervention arms in a 1:1 fashion.

In this situation, where Length of Stay is less than the initially estimated >7 days, we further assume that each individual, will, on average, have a length of stay of 5.5 days on the Burn ICU thus resulting in 11 wound care procedures

performed during hospital stay on the Burn ICU. We determined the minimum sample size for our trial based on 80% power at p = 0.05 to detect a clinically significant difference in mean pain score during the wound care procedure of 2.0 between the control and intervention arms with a standard deviation of 4.0. In addition, to account for the clustered nature of procedures performed on individuals, we have used a sample size inflator (also termed "design effect") of 8.0 as described by the Cochrane manual@ conservatively using an interclass correlation of effects of 0.7 amongst repeated measures of pain scores within each individual and 11 observations per individual.

The required sample size needed to accept the alternative hypotheses that the mean pain care score in the intervention arm decreased by 2 points compared to the control arm at the 0.05 level would require 47 eligible individuals (94 total), our anticipated population of 128 eligible individuals is adequate to show a clinically significant improvement for both intervention arms.

@http://handbook.cochrane.org/chapter\_16/16\_3\_4 approximate analyses\_of\_cluster\_randomized\_trials\_for\_a.htm

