#### **Changes Requested:**

- a. Inclusion and length of stay clarifications:
  - The length of stay for our protocol had been set at ≥7 days estimated at time of admission to the burn center. However, the number of days a patient remains in the BURN ICU is highly variable, and dictated by factors difficult to accurately quantify when first admitted. For example, patients leave against medical advice, to seek drugs or alcohol, to return to work, or attend to financial matters. For example, some patients may leave the BURN ICU earlier than was originally estimated due to faster wound healing. Others may proceed to the OR for surgical closure of the wounds prior to 7 days, which typically changes the type and duration of wound care for several days after surgery. The length of ICU stay of others may decrease due to an initial overestimate of wound severity and, hence, a reduced need for close ICU monitoring and a reduced likelihood that the patient would remain in the BICU for 7 or more days.
  - b. Inclusion requirement clarification 1: While retaining the inclusion criteria as estimated LOS  $\geq$ 7 days at time of admission, we request a Change in Research such that the actual minimum number of days spent on the BICU be changed to achieve an average LOS of  $\geq$ 5.5 days. The actual number of wound care sessions is to range from 3-7 days and the range in sessions to be from 3 (1/day for 3 day length of stay) to 14 (2/day days at 2 sessions/day plus 1 session on last day), respectively.

These two ranges (i.e., average LOS  $\geq$ 7 days, average LOS  $\geq$ 5.5 days) were used in estimating two sets of power estimates, sample size and in participant accrual. However, data will be considered on an intent to treat basis for those participants with less than 7 treatment days and less than 14 wound care sessions due to abbreviated stay on ICU, surgery for wound closure that obviates further wound care, or who are discharged early.

C. Inclusion requirement clarification 2: Similarly, there are some patients who are ordered to receive only one dressing change per day rather than the usual two per day, while, rarely, some may be scheduled for 3 wound care sessions on certain days. Data on any participants who are otherwise eligible for the Ketamine Trial but who are ordered to have daily wound care procedures  $\geq 2/day$  or  $\leq 2/day$  will be considered on an intent to treat basis.

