Statistical and Database Management Resource: The ICTR is highly regarded for database development incorporating multiple layers of protection. The Director of the ICTR, [name], trained and supervised the Ketamine Team in developing the REDCap database to enter, save, protect and prepare to export for analysis, the data generated in this project. The benefits of the REDCap database include: firewall behind the existing JHU firewall, establishing restricted and unrestricted accessibility modes to ensure IRB protected data remain accessible only to individuals listed on the IRB, compartmentalizing tasks, and running the latest antiviral and anti-hacking software. Data integrity is assured using multiple methods, including utilizing variable definitions and data dictionary (item name and definition, scale, range, out of range and multiple key hit detectors). The complexity of this database is necessitated by the elegant and rigorous study design with 14 repeated measures over 7 consecutive days, which will entail multilevel analysis of time varying and time invariant data. Each variable is coded by day (1-7) and session (1-14), as well as data input quality such as double entry, blinded data collection and data entry, automated checks, auto scoring programs, time lapse between recording and entry, standardized data collection forms, and, enhanced study-specific Manual of Operations for the Safety, Efficacy and Opiate-Sparing Effects of Ketamine for Acute Burn Wound Care Pain in a Setting Analogous to Austere Battlefield Conditions (IRB00089761). The Manual was adapted from a previously developed Manual that was successfully utilized by [name] and his team for Management, Operations, and Evaluating Progress towards Goals. It contains a wealth of detailed information that identify topics covered, specificity of instructions for involved personnel, roles, tasks, timelines, procedures and to ensure adequacy of documentation.

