Group assignment will be based on serial admissions meeting study inclusion / exclusion criteria. Randomization as described above is expected to achieve group equivalence in: 1) the first pain severity score obtained using the Numeric Analogue Scale measured during the1st exam prior to the first wound care session in the Burn Center; 2) the TBSA; 3) the need for surgery; 4) the average length of wound care procedures and; 5) "other" variables, including the distribution of baseline symptom severity of acute stress disorder, depression, anxiety, and insomnia (which will all be assessed at study enrollment before the first target dressing change). Baseline data on participants will be recorded, and comparability between study groups will be examined at 25% (n=  $\sim$ 19-24/group) and 50% (n=  $\sim$ 37-47/group) of study completion to assess presence of balancing issues. These same data will also be examined upon study completion (n= 74-94), and their relationship with core outcome targets will be examined. If necessary, their effect will be taken into consideration in planned analyses.

It is anticipated that, given the large sample size, the process of random assignment will ensure adequate balancing across study conditions (Usual Care Condition, Usual Care PLUS Ketamine Augmentation Condition) of potentially confounding variables. That is, for example, participants differing by clinically important variables such as smaller versus larger burns should be equally represented in both groups. The large sample size and the process of random assignment are deemed more than adequate to ensure representation across the two study arms for the differences in important but extraneous variables such as procedure duration and other aspects of wound care, rehabilitation and surgery.

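### The dropout rule treats the last data obtained as the endpoint for participants whose wound care ends early, which conflicts with the mean-over-sessions pain endpoint on which the trial is powered

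*Combined protocol and SAP*

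**What the plan says.** **Powered endpoint.** Both sample size estimates (Sample Size and Power Estimations, items 1 and 2) say that the primary procedure tests "the difference in mean pain scores, defined as the average self-report of mean pain score" during the burn wound care procedures. Item 1 assumes 14 procedures per participant and a difference of "2.0 points between the control and intervention arms with a standard deviation of 3.0". Item 2 assumes 11 procedures and an SD of 4.0. Both apply a design effect "to account for the clustered nature of procedures performed on individuals", with a within-participant correlation of 0.7.

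**Dropout rule.** Section 7, Participant Dropout, covers two groups: dropouts, and participants whose wound care ends or changes substantially before the 7-day period is over. They are handled by intention to treat "in all key analyses with the last data obtained treated as the endpoint for that participant".

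**Other text on short stays.** Changes Requested, item b, expects "the range in sessions to be from 3 (1/day for 3 day length of stay) to 14" and says that "data will be considered on an intent to treat basis for those participants with less than 7 treatment days". The database paragraph that follows describes 14 repeated measures, "which will entail multilevel analysis of time varying and time invariant data". The Data Analysis Plan leaves ANCOVA or longitudinal growth modelling open. It describes ANCOVA as a method for change from before to after treatment, adds that it can handle repeated measures, and expects little dropout.

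**The concern.** A last observation and a mean over sessions are different endpoints. The dropout rule names the first, for all key analyses. The sample size is built on the second. No passage says how one is to be fitted to the other.

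Taken literally, the rule can mean either of two things for a participant whose care ends early:
- one last value is the outcome, while participants who complete 7 days contribute the mean of all their sessions; or
- the last value is carried into the remaining scheduled sessions, so that procedures never performed receive a pain score.

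A third reading, that the participant's series stops at the last observation and all of it is used, is harmless and fits the rest of the plan. The paragraph does not state it. The phrase intention to treat settles who is analysed, not what is measured on them.

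Two things are at stake. The primary pain outcome is not uniquely defined for a possibly large part of the sample, so the reading could be settled after results are known. The single-value reading also discards sessions that were observed. The rule is not limited to withdrawals, because it also catches participants whose wound care simply finishes.

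**Working it through.** **Inputs.** Difference 2.0; SD 4.0 with 11 sessions, or SD 3.0 with 14; correlation (ICC) 0.7; 80% power at 0.05; 1:1 allocation (sample size items 1 and 2). Sidedness is not stated. Two-sided is used because it reproduces the plan's figures; one-sided gives about 37 per arm where the plan has 47.

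**1. The plan's own figures.** The design effect is 1 + (m − 1) × 0.7, which is 8.0 for m = 11 and 10.1 for m = 14. A two-sided t-test needs 64 per arm at SD 4 and 37 at SD 3.
- SD 4: 64 × 8.0/11 = 46.5, so 47 per arm (94 in total), as stated.
- SD 3: 37 × 10.1/14 = 26.7, so 27 per arm (54 in total), as stated.

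Multiplying by design effect/m is the same as giving each participant an outcome with variance SD² × (0.7 + 0.3/m). The stated sample size therefore rests on every participant contributing all sessions.

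**2. How many might fall under the rule.** Table 1 (Burn Center 5-year average) gives annual averages of 128 admissions with a stay of at least 5.5 days and 74 with at least 7 days. That leaves 1 − 74/128 = 42% with 5.5 to under 7 days. Pooling the four full years 2012–2015: 1 − 326/534 = 39% (35% to 43% by year).

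**3. Early enders scored on one last session.** With share f affected, the outcome variance is f × SD² + (1 − f) × SD² × (0.7 + 0.3/m). Power for 2 points, N=94:

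| | f = 0 | f = 0.20 | f = 0.42 |
|---|---|---|---|
| SD 4, m = 11: effective SD | 3.411 | 3.537 | 3.670 |
| SD 4: power | 80% | 77% | 74% |
| SD 3, m = 14: effective SD | 2.548 | 2.645 | 2.747 |
| SD 3: power | 96% | 95% | 94% |

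At N=100, the raised target in section 7c, SD 4 gives 83%, 80% and 77%. The loss depends on the ICC. At SD 4, N=94 and f = 0.42, power falls from 90% to 80% if the ICC is 0.5 and from 71% to 69% if it is 0.9.

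**4. Last value carried forward to 14 sessions, then averaged.** With k sessions observed, the last has weight (15 − k)/14 and the others 1/14. The variance is SD² × (0.7 + 0.3 × S), with S = [(k − 1) + (15 − k)²]/196. The comparator is each participant's own mean, SD² × (0.7 + 0.3/k). The other 58% have 14 sessions. SD 4, N=94, 42% affected:

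| Sessions observed (k) | S | Own mean | Carried forward | Loss |
|---|---|---|---|---|
| 11 | 0.133 | 80.5% | 80.2% | under 1 point |
| 6 | 0.439 | 80.0% | 78.1% | about 2 points |
| 3 | 0.745 | 78.9% | 76.1% | about 3 points |

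**5. All observed sessions used.** The own-mean column shows that short series cost little by themselves: power is still 79% if the 42% had only 3 sessions each.

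**Assumptions throughout.** A constant 2-point effect, equal correlation between sessions, no trend over sessions, the same share affected in both arms, and no baseline adjustment.

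**The case against.** The strongest reply is that the weight of the text favours the harmless reading. The sample size items define the endpoint as a mean over sessions, the database paragraph foresees multilevel analysis, the Data Analysis Plan names growth modelling, and short-stay data are kept by intention to treat. This stands as a reason to think that the conflict is one of wording. It does not remove the conflict, because the dropout paragraph is the only one that states an endpoint for these participants, and it states a different one for all key analyses.

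The size is also conditional. Baseline adjustment, which ANCOVA would bring, is left out of the power figures. At SD 3 every figure above stays at 94% or more at N=94. The 42% is a registry proxy: keeping an estimated stay of at least 7 days at admission could lower it, and surgery or stays below 5.5 days could raise it. All of this stands.

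Three stronger readings are tempting, and the documents support none of them.
- *Everyone is scored on a final value.* That would give 67% power at SD 4 and N=94. It would come from the Data Analysis Plan's mention of pre-to-post change, not from the dropout rule, which covers only early enders. The same sentence of the Data Analysis Plan says that ANCOVA can be used for repeated measures.
- *The sample size is wrong.* It reproduces. The fault is that the dropout rule is not tied to it.
- *The rule biases the result in a known direction.* That depends on how pain changes over sessions and on whether early ending differs by arm. The documents give neither.

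**Conclusion.** The point holds as a conflict between the dropout rule and the powered pain endpoint, and it should be fixed before unblinding. Of the readings considered, only the use of all data up to the last observation agrees with the sample size calculation, and the plan does not say that this is meant.

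The cost in power is moderate. Under the assumptions listed with the calculation, scoring early enders on one last session costs about 6 points at SD 4 and 2 at SD 3 if 42% are affected, and about 3 and 1 if 20% are. At SD 4 with 42% affected, the loss ranges from 2 points (ICC 0.9) to 10 points (ICC 0.5). Carrying forward costs at most about 3 points in the cases computed; the objection to it is mainly that it scores procedures that did not happen. Confidence is high that the rule and the endpoint do not fit together, and lower for the exact losses, since the share affected is not stated.

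**What to change.** Delete the last-value rule for both primary aims and state the following.

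- **Aim 1 (pain).** Primary pain is analysed from session-mean NAS over every session performed, for every randomised participant with at least one session. Use one mixed model with arm, session number, baseline NAS and a patient random intercept. Baseline is the Burn Center score that the Randomization text already identifies ("the first pain severity score obtained using the Numeric Analogue Scale"). Nothing is carried forward after wound care ends.
- **Aim 2 (opiate sparing).** Analyse requests per session performed, over all sessions performed, with no last-value substitution and no unadjusted sums, because sums also reflect how many sessions took place.
- **Changed wound care.** Keep sessions after surgery or another substantial change in the primary analysis, and add a sensitivity analysis that excludes them.
- **Data Analysis Plan.** Align the wording on change from before to after treatment with the mean-over-sessions endpoint.

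The session term is needed because series differ in length. If pain fell by an assumed 0.1 to 0.2 points per session, means over 6 and over 14 sessions would differ by (7.5 − 3.5) × 0.1 to 0.2 = 0.4 to 0.8 points with no drug effect.

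The cost is a few sentences of SAP wording and one sensitivity analysis. Data are already coded by day and session, so no new data or participants are needed.

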# d. Early stopping rules.

See "Definition of treatment failure or participant removal criteria", above.

# 8. Risks

a. Medical risks, listing all procedures, their major and minor risks and expected frequency.

Ketamine: The risks of low-dose, slow infusion ketamine have recently been reported in several ED Trials reviewed in updated risk / benefit sections above and in summary of changes made. The major disadvantages to using ketamine as a single agent in small or large doses, or when administered rapidly (<1 minute) are altered perceptions occurring commonly and characterized as floating sensations, vivid dreams, hallucinations and delirium. The consequence of these untoward side effects in a combat theater of operations is currently undefined.

One recent retrospective review of ~400 patients (patients 30% acute pain, 70% post-op) found significant drop in pain but also a significant increase in hypertension and hypotension in patients provided ketamine plus opiate analgesia (Kator, 2013).

Procedural Risks: The twice daily wound care involve debridement of necrotic tissue, cleansing raw wounds and related activities and tasks. The risks of pain, infection and distress associated

with these procedures will not differ among participants assigned to either group – prior to the first study procedure. The study aims involve testing whether the study drug reduces pain and distress during the procedures as a direct effect of the study drug. The study inclusion criteria require that a certain moderate-severe pain be present prior to study onset in order to be able to discern differential efficacy in pain reduction across study conditions. There is no risk of greater pain, rather, it is anticipated that the usual care group runs the risk of experiencing less pain relief than the study drug group. It is not being evaluated, but it is not anticipated that there will be differences between consented participants and eligible but non-consenting participants.

All patients enrolled in the study will be patients at the Burn Intensive Care Unit (BICU) and will be under the ongoing care of the Burn Surgery and Critical Care Medicine Services. All patients in the BICU are at risk for delirium from multiple sources and are assessed and monitored for this condition as part of regular nursing and physician assessments of the patient's mental status. However, to address the question regarding the possibility that subjects who receive Ketamine will have a higher incidence of hallucinations/delusions, we will keep a daily tally of such experiences in subjects' research charts (i.e., the presence or absence of hallucinations/delirium in addition to the severity of these symptoms, should they exist) using the Side Effect Measure of Opiates and Ketamine (see Measures) as well as a list of other potential causes of the delirium / hallucinations (e.g., benzodiazepines, alcohol withdrawal). We will conduct post hoc analyses to address the relative frequency and severity of these phenomena in the ketamine versus usual care "control" arms of the study.

b. Steps taken to minimize the risks.

Assessments: Twice during each shift, all patients on the BICU are scored using the nurseadministered CAM-ICU and the RASS. These are recorded in EPIC and changes reported to providers and to the following shift. The study team will assess potential side effects using the patented Side Effect Measure for Opiate and Ketamine (SEM-OK; Janssen). The SEM-OK will be administered prior to day 1, session 1, and after session 1 on days 3, 5 and 7. The RA and the Co-Investigator provider present will rate the SEM-OK.

Low-Dose, Slow Infusion Ketamine: In order to minimize the psycho-mimetic risks, the ketamine+UC will be delivered in a sub-anesthetic, low dose, slow infusion preparation (see above). The dose, route, duration time of infusion have been established per study protocol and as prescribed by and monitored by the study Co-PI ([name], CCAM), the JHBMC Pharmacist ([name]), Burn Center anesthesiologist ([name], CCAM), Burn Center attending surgeon ([name], Burns & Plastic Surgery), or, under the direct, supervisory and evaluative authority of these physicians, the Burn Fellows, or the burn center mid-level providers (PA, NP) and as monitored by the professional nursing staff of the Johns Hopkins Burn Center. The psycho-mimetic risks will be monitored as noted above using the Side Effect Measure of Opiates and Ketamine (see Measures).

3.

Pharmacy's role in policy decision-making with JHBMC Pharmacy and Therapeutics as well as in preparing the drug and delivery system.

i. JHB Pharmacy and Therapeutics Policy - discussed ketamine for research purposes in clinical setting, arrived at definitive decision in consultation with research pharmacist [name] at JHBMC and the results of her discussion with [name], Director of Interventional Research Pharmacology at JHBMC.

ii. The Ketamine Project team is adding [name] as Co-Investigator on the project for the role and tasks delineated here.

[name] has completed the "Drug Build" for the project. Specifics will be provided. She and [name] (see next) collaborate on the "Order Build" and "Drug Build" to ensure the accurate and timely delivery of study drug to study participants. The study drugs (Ketamine as well fentanyl and saline) will be delivered in plain, nondescript identical delivery system for both study drug and usual care preparations. This allows blinding of provider/prescriber, nurse and patient.

iii. The IRB-approved protocol was presented by [name] at the January 2017

JHMBC Pharmacy & Therapeutics Committee (P&T) meeting for approved use in hospitalized patients. The process for approval of clinical policy versus IRB-approved protocols are through the same committee. Full approval was given at the next P&T Committee meeting by all necessary governing bodies for the use of ketamine in this IRBapproved protocol. The pharmacy and [name] in particular, will continue to work with the Ketamine study team to coordinate provision of study materials in a blinded fashion as described next.

iv. Once the Ketamine Project Management Team identifies and consents a participant, the pharmacist will then randomize the subject based on the schema provided by the ICTR database and statistician as described above. Based on group assignment, the pharmacy will prepare the appropriate medication / placebo / study drug, deliver this to the BICU in identical bags labeled in a blinded fashion. Despite being blinded, the label will include all elements required by law.

[name] Clinical Research Pharmacist Johns Hopkins Bayview Medical Center [name]

[name] has begun the "Order Build" for the order set to be entered in the BICU EPIC. [name], Application Coordinator III Johns Hopkins Health Systems [contact]; IT@jh EPIC

5. Training House Staff and Nursing on Ketamine Protocol

[name], DNP: Nurse Manager for the JHBMC Johns Hopkins Burn Center and the Surgical Intensive Care Unit. Scheduled Dates of Training Completion –

Overview and Discussion: Monthly Nursing Staff Meeting - 30 February 2017

Didactics & Hands-On: Monthly Nursing Staff Meeting - 29 March February 2017

See Powerpoint Education Tool – attached.

[name] approved the involvement of nursing personnel in the following aspects of the Ketamine Trial. She described the manner in which the training in the protocol would be best conducted initially on 2/30/17 at the regularly scheduled nursing team meeting (handouts, posters using graphic and verbal modalities) to provide an overview of study aims, background mechanisms and rationale for the study and to address any questions. A more detailed and hands on training covering the specific steps of nursing involvement that is scheduled for nursing staff at subsequent meeting. Follow-up discussions will be conducted at the next nursing staff meeting to discuss individual nurse experiences with the study and to address any questions or concerns that may have arisen in the course of study start-up.

JHBMC Nursing Policy for Ketamine (sub-anesthetic, slow infusion, analgesia for severe, acute burn pain during wound care):

- The Ketamine for Managing Acute Wound Care Pain study stipulates that the RNs will hang and initiate the infusion of the ketamine at rates pre-programmed into the infusion pump.
- As described above, the study drug will be prepared by the pharmacy at JHBMC when the provider orders it for a study participant. The container for delivery of the infusion will be identical for ketamine and saline preparations and, thus, will allow for a triple-blinded (provider, nurse, patient, RA) and randomized manner. All participants will receive usual care fentanyl, while half of the participants will receive saline infusion and the other half of the participant sample will receive ketamine – both as described above. Under the study design, the provider, nursing staff, study staff, and participants will not know which participants receive "ketamine + UC / fentanyl" or "UC / fentanyl + saline".
- RNs will not administer or adjust loading dose or infusion rate these will be preset by pharmacy in
  nondescript delivery mechanisms. Infusion pumps for both the Usual Care Group (Saline infusion) and
  the Usual Care Plus Ketamine Augmentation Group (Ketamine infusion) will be programmed to
  administer a Loading Dose/infusion of saline for the usual care condition and a Loading dose/infusion
  of ketamine in the Usual Care PLUS Ketamine condition at 10 minutes prior to onset of wound care.
  Both conditions will receive usual care fentanyl at < 1 minute prior to wound care onset. Then, the
  Usual Care Condition will receive a slow infusion of saline beginning after the saline loading dose

infusion ends throughout the wound care until the session ends, and the ketamine plus usual care condition will receive a slow infusion of low dose ketamine starting after the loading dose ketamine ends and continuing on through until the end of the session. These are described in Table 1 and in the text following Table 1, above.

- The ketamine loading dose and the session length infusion will deliver a sub-anesthetic/low dose at a slow rate and neither are expected to cause significant changes in vital signs, including respirations.
- RNs will not titrate or adjust the dose of ketamine (or saline placebo) as all doses are preset as
   determined under the study protocol and the delivery pump is preprogrammed by the study
   pharmacist and delivered to the burn center where it will be administered to the participant. The
   prescribing provider, RA, the nurse, and the patient will be naïve to the contents of the pump being
   administered.
- RNs will monitor participants as per standard of care and closely monitor them for the effects of the drugs administered as per standard of care for all patients in the BICU (i.e., each patient is rated twice per shift using the CAM-ICU and RASS).
- RNs are expected to administer PRN doses of fentanyl titrated to the patient's perception of pain consistent with their usual practices for wound care. In the case of this Trial, pain rated by the patient as low moderate "despite routine treatment" (Lee and Lee, 2016). The PRN is the BICU standard of care fentanyl PRN Dose = 1 mcg / kg (0.07 mg in a 70 kg individual). This criteria for providing PRN fentanyl is within the range of customary/usual care BICU nursing practice and is provided to participants in either Group 1 or Group 2 when a participant requires additional pain medication as described here and above.
  - a. As above, all subjects will be under the ongoing care of the Critical Care Medicine and Burn Surgery Services. In the unlikely a patient becomes hemodynamically unstable during the study, the CCM and/or the Burn Surgical Services would immediately note the alarm and they would initiate an emergency response. The study investigators would be notified in a timely manner regarding any such occurrences and this would be evaluated and reported to the IRB, DoD HRPO and to the NTI.
  - b. Our intention is not to exclude participants with hypo- or hypertensive co-morbidities as in order to potentially decrease this risk. Ketamine has been long regarded for its superior hemodynamic stability as compared to other analgesic/sedative medications and such crises are unlikely. Furthermore, the Ketamine for Acute Burn Pain study will employ low doses of ketamine and infused it so slowly that it is unlikely to induce hemodynamic instability.
  - c. Of note, the clinical experience of the attending surgeon and critical care / anesthesiology attendings using low dose ketamine in burn patients also indicate that ketamine is not associated with hemodynamic instability. All prospective patients will have sustained serious burn wounds requiring ongoing wound care. This wound care requires sedative/analgesic medications for pain management. One intention of the current study is to demonstrate the efficacy in providing analgesia during the ongoing wound care; this hypothesizes that the adjunctive use of ketamine will afford less hemodynamic instability and fewer adverse events or drug side effects compared with conventional sedative/analgesic regimens.

